Breast density is also associated with advanced cancer presentation: in a cross-sectional analysis of tumor characteristics in 546 women diagnosed with invasive breast cancer, women with a tumor size >1.0 cm were more likely to have dense breasts compared with women with a tumor size ≤ 1.0 cm after adjusting for confounders.¹⁵ Breast density is also the primary factor associated with the presentation of an interval cancer, defined as breast cancer diagnosed within 12 months of a negative screening mammogram². The odds ratio for an interval cancer is 17.8 for women with mammograms defined as having $\geq 75\%$ density compared to those with $<10\%$ density.¹² When characteristics of interval cancers are compared in women with dense breasts (defined as $\geq 25\%$ density) vs. those with $< 25\%$ density, tumors in dense breasts were more likely to be larger ($P < 0.001$) and have lymph node metastases ($P = 0.001$). However, there were no differences in proliferation rates between interval and screen-detected cancers in dense breasts, suggesting that interval-detected cancers in women with dense breasts are larger not because they are more biologically aggressive, but because of a delay in detection. The hazard ratio for breast-cancer specific mortality was three times higher for interval cancers compared to screen-detected cancers, but this association disappeared in the dense breast group after adjusting for tumor size.¹⁶ This evidence suggests that detecting tumors at a smaller size in women with dense breasts would have a significant mortality benefit.

Breast density legislation has provided an important mechanism of informing women about the implications of breast density in masking cancers on mammography. Most state-mandated breast density letters contain language encouraging women to “use this information to discuss with your health care provider whether other supplemental tests in addition to your mammogram may be

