2.2 Secondary Endpoints

Secondary Endpoints include the following:

1. To compare the invasive cancer detection rates of DBT alone vs. MBI alone at Year 1 screening.
2. To compare the screening performance metrics of sensitivity, specificity, recall rate, biopsy rate, positive predictive value and negative predictive value for DBT and MBI.
3. To compare tumor characteristics of all cancers (invasive and noninvasive) detected on DBT and MBI, including size, nodal status, and molecular subtype.
4. To assess the reduction in advanced cancer rate with incorporation of MBI screening by comparing advanced cancer rate observed at Year 2 screening relative to that at Year 1.
5. To assess the rate of interval cancers with incorporation of MBI screening.
6. To examine the relative performance of DBT and MBI within subgroups categorized by breast cancer risk.

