7. DURATION OF FOLLOW-UP

Study participation involves 2 study visits for breast screening – one at the beginning of the study and a second visit one year later. Participants will be enrolled in the study for approximately 2.5 years (30 months) to ascertain breast cancer status, and may be contacted at the end of study if breast cancer status cannot be ascertained based on chart review, alone. If only one of the baseline

imaging tests (DBT or MBI) is completed, the patient will be excluded from the study and no data will be collected. Participant's breast cancer status will be obtained from chart review or patient contact targeted for 365 days after each screening year, but may be obtained from 335 days to 455 days after screening, unless the patient specifically requests to withdraw from the study. If a patient is diagnosed with a primary breast cancer during the study period, no subsequent follow-up or further study imaging will be required for this research study.

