Predictive values will be estimated for each modality based on data pooled across radiologists. PPV1 (the proportion of patients with breast cancer among patients with abnormal screening examinations), PPV3 (the proportion of breast cancers diagnosed among biopsies performed), and NPV (the proportion of patients without breast cancer among those with normal screening examinations) will be determined. The primary unit of analysis will be the patient, except for PPV3, in which the primary unit of analysis will be the biopsied lesion. The method of Moskowitz and Pepe will be used to compare relative

predictive values between the two imaging modalities.³⁷ Secondary analyses may adjust for clustering of results within radiologist.

3. To compare tumor characteristics of all cancers (invasive and noninvasive) detected on DBT and MBI, including size, nodal status, and molecular subtype.

The analysis comparing tumor characteristics will be descriptive. Size, nodal status, and molecular subtype (including estrogen and progesterone receptor status, HER-2 status, Ki-67 and Oncotype DX score as available) will be abstracted from clinical final pathology reports from all biopsies and surgeries performed. The distribution of sizes will be summarized by ordinary numeric (e.g., means, SDs, range) and graphical (e.g., histograms, density smoothers) summaries. Descriptive summaries of the lesions identified with MBI but not DBT and vice versa will also be calculated to understand the differences in performance should one be identified.

4. To assess the reduction in advanced cancer rate with incorporation of MBI screening by comparing advanced cancer rate observed at Year 2 screening relative to that at Year 1.

For the purpose of our analysis, advanced cancers are defined as cancers greater than 2 cm in maximum dimension (determined by measurements on pathology or imaging) and/or cancers that are lymph node positive, as these patients may be considered for neoadjuvant chemotherapy. To assess whether the incorporation of MBI screening reduces **advanced cancer rate**, the rate of advanced cancers detected at Year 2 screening will be compared to the rate at Year 1 screening. The rates of advanced cancers, together with their respective 95% confidence intervals, will be estimated for Year 1 and Year 2. Comparison in the rates between Year 1 and Year 2 will utilize the test of two proportions based on exact binomial distributions.

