5. To assess the rate of interval cancers with incorporation of MBI screening.

For the purpose of our analysis, interval cancers are defined as cancers diagnosed not at study imaging but between Year 1 and Year 2 screening tests. The interval cancer rates per 1000 women screened will be determined as the proportion of participants in the analysis set who had an interval cancer diagnosed and verified by pathology. To assess whether the incorporation of MBI screening, with one year of follow-up for breast cancer results in a “low” interval cancer rate, we will compare the interval cancer rate found in our study to the reported interval cancer rates for a population of women with dense breasts.

Per Breast Cancer Surveillance Consortium (BCSC) analysis³⁸ the interval cancer rate among women with dense breasts was 89 per 100,000 women (or ~0.9 per 1000). The authors of this analysis considered an interval cancer rate greater than 1 case per 1000 mammography examination as an unacceptable performance level. We will estimate the rate of interval

cancers from our study and provide a 95% confidence interval. The performance level of this screening approach will be considered unacceptable if the lower bound of the confidence interval exceeds 1/1000 (i.e. 7 or more interval cancers in this cohort).

6. To examine the relative performance of DBT and MBI within subgroups categorized by breast cancer risk.

The comprehensive risk factor collection planned in this study will allow accurate risk estimation promoting generalizability of results by type of risk model and level of risk. As an exploratory analysis, we will examine if the risk estimates determined with Gail, BCSC, Claus, and Tyrer-Cuzick models may predict a subgroup of women with MDB who are more likely to benefit from a specific supplemental screening. In particular, the relative performance of the screening modalities (sensitivity and specificity) will be characterized separately, within subgroups of patients defined by various levels of risk. The statistical power to discern differential performances of the screening modalities among different risk subgroups may be limited due to the restricted sample size in these subgroup analyses.

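### The advanced-cancer comparison counts only screen-detected cases, so on its own it cannot support a claim that MBI lowered the advanced cancer rate

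*Combined protocol and SAP*

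**What the plan says.** Section 2.2, item 4 gives the objective: "To assess the reduction in advanced cancer rate with incorporation of MBI screening". The yardstick named there is the rate seen at the second screen set against the first. Section 8.6, item 4 repeats the aim and sets the analysis: "the rate of advanced cancers detected at Year 2 screening will be compared to the rate at Year 1 screening". For this purpose "advanced cancers are defined as cancers greater than 2 cm in maximum dimension", or node-positive, or both; the definition has no rule on how the cancer came to light. On the test, "Comparison in the rates between Year 1 and Year 2 will utilize the test of two proportions based on exact binomial distributions". Item 4 states no expected rate, significance level or power.

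Cancers found between screens have their own endpoint. Under section 8.6, item 5, "interval cancers are defined as cancers diagnosed not at study imaging but between Year 1 and Year 2 screening tests". They are reported as one total with a 95% confidence interval, and performance is called unacceptable at 7 or more. There is no split by advanced status and no link to item 4.

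On what happens after a diagnosis, section 7 says: "If a patient is diagnosed with a primary breast cancer during the study period, no subsequent follow-up or further study imaging will be required".

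**The concern.** The aim concerns the advanced cancer rate; the analysis concerns advanced cancers found at a screen. The two come apart for a woman whose cancer is missed at Year 1, or grows quickly after it, and is diagnosed node-positive some months later. She has an advanced cancer after MBI was introduced, yet she is absent from the Year 2 rate. A failure of the first round can thus help the rate that is meant to show the benefit.

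The protocol's own rationale makes such cases plausible. Section 1.1 argues that "interval-detected cancers in women with dense breasts are larger" because they are detected late, and size above 2 cm is one of the two criteria for advanced cancer. Section 1.5 presents the change in advanced cancer presentation over two annual MBI scans as a first for this study, so the result is likely to be quoted.

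**Working it through.** **Step 1: where an advanced interval cancer goes.** Reading the sections together:

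- Section 8.1.2 (Year 1 reference standard): a cancer diagnosed after Year 1 screening and before Year 2 screening gives positive status for Year 1.
- Section 5.1: only women without a breast cancer diagnosis during Year 1 go on to Year 2 MBI.
- Section 7: no further study imaging is required after a diagnosis.
- Section 8.4: the analysis set for a year requires both DBT and MBI in that year.

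Such a cancer is therefore in neither the numerator nor the denominator at Year 2. One sentence in item 4 speaks more loosely of estimating advanced cancer rates for Year 1 and Year 2. If that were read to include interval cases, section 8.1.2 would put them in Year 1, still not on the post-MBI side. No sensitivity analysis moves them.

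**Step 2: the plan's own figures.** Item 4 has none, so I checked the two that set its scale.

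- Evaluable sample size (section 8.7): n = 2631, 0.001 versus 0.004, one-sided exact binomial test at 0.025. Rejecting at 7 or more gives P(X ≥ 7 | 0.001) = 0.0181 and P(X ≥ 7 | 0.004) = 0.9001. With n = 2630 the power is 0.8998. The figure reproduces.
- Interval-cancer cut-off (section 8.6, item 5): the exact two-sided 95% lower bound at n = 2631 is 1.07 per 1000 for 7 cases and 0.84 per 1000 for 6. The cut-off reproduces, so at that n up to 6 interval cancers, whatever their stage, stay below the threshold.

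**Step 3: expected interval cancers.** The registry rate cited in item 5 is 89 per 100,000.

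- 2631 × 0.00089 = 2.3
- 3006 × 0.00089 = 2.7

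These are cancers of any stage. The documents do not give the advanced share. Each case left out lowers the post-MBI rate by 1/2631 = 0.38 per 1000.

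**Step 4: effect on the comparison.** The documents give no advanced-cancer rate, so all counts here are assumptions. I used n = 2631 in each year and Fisher's exact two-sided test.

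| Assumed Year 1 vs Year 2, screen-detected | p as planned | p with 1 interval case added to the post-MBI side | p with 2 added |
|---|---|---|---|
| 8 vs 1 | 0.039 | 0.109 | 0.226 |
| 10 vs 2 | 0.038 | 0.092 | 0.179 |
| 12 vs 2 | 0.013 | 0.035 | 0.076 |

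For 10 versus 2, the post-MBI rate goes from 2/2631 = 0.76 to 3/2631 = 1.14 or 4/2631 = 1.52 per 1000, against 10/2631 = 3.80 per 1000 at Year 1.

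**Step 5: two other ways of booking the cases, from 10 versus 2.**

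- Adding them to Year 1 only, as section 8.1.2 would: 11 vs 2 gives p = 0.022 and 12 vs 2 gives p = 0.013. The apparent reduction grows.
- Adding the same number to each round: 11 vs 3 gives p = 0.057 and 12 vs 4 gives p = 0.076. The absolute difference stays at 8/2631 = 3.0 per 1000; the ratio moves from 0.20 to 0.27 or 0.33.

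**The case against.** The best defence is that like is compared with like. Section 3.1 admits only asymptomatic women, so cancers that surfaced clinically before entry are outside the Year 1 rate as well. Both rates are screen-detected, and a first round against a second round is a reasonable way to ask whether the reservoir of occult cancers described in section 1.5 has been drawn down. This stands. A reader might infer that the comparison itself is invalid or biased; as a comparison of two screen-detected rates it is not. The gap lies between that quantity and the stated aim.

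Second, interval cancers are not hidden, because item 5 counts every one and has a decision rule. This stands in part. A shift from screen to interval presentation would raise that total, but the total does not show how many were advanced and does not feed into item 4.

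Third, a reader might infer that the Year 2 rate is undercounted by some 20 to 30%. That needs two assumptions that the documents do not supply: that half of 2.7 interval cancers are advanced (1.35), and that 3 to 5 advanced cancers are found at the Year 2 screen (1.35/4.35 = 31%; 1.35/6.35 = 21%). It also looks at Year 2 alone, and the registry rate is an outside comparator, not a rate after MBI.

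Fourth, it is tempting to think that counting each screen together with its following year under section 8.2 settles the matter. It does not. Those windows assign first-round misses to Year 1, and if both rounds gain equally the absolute difference is unchanged.

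**Conclusion.** The point holds in a limited form. As written, item 4 can show a fall in screen-detected advanced cancers between rounds. By itself it cannot support a statement that the advanced cancer rate fell with MBI, because advanced cancers presenting between the screens never count against the post-MBI rate.

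The direction follows from the text. The size does not: it depends on the number of advanced interval cancers and on the advanced-cancer rates, neither of which the documents give. Under the assumed counts in the working, one or two cases are enough to lose nominal significance, though not in every case (12 versus 2 with one case added stays at p = 0.035). A reader might go further and infer that any reduction seen at Year 2 would be spurious; nothing in the documents supports that. This is a secondary endpoint and the remedy is cheap, so it is an improvement worth making and no threat to the primary result.

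**What to change.** In section 8.6:

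1. Keep the item 4 comparison and label it as the rate of screen-detected advanced cancers.
2. Prespecify a sensitivity analysis. The post-MBI rate is advanced interval cancers between Year 1 and Year 2 plus advanced cancers at Year 2 screening, over all women at risk after Year 1 screening. Compare it with the Year 1 screen-detected rate. Report how many of these women did not attend Year 2 screening, since they can contribute interval cancers only.
3. Report the item 5 interval cancers by advanced status.
4. State that a reduction will be claimed only if both analyses agree in direction.

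A count per screening year, treating both rounds alike, may be added as supportive. Section 8.2.2 must be corrected first: its Year 2 window runs from Year 2 screening to a next screen also labelled Year 2, and it gives negative Year 2 status to a cancer detected at Year 2 screening. This count does not replace the analysis in point 2.

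Cost: SAP wording and a little analysis. Item 3 of section 8.6 already abstracts size and nodal status from pathology reports, and follow-up to Year 2 already identifies the interval cancers. The downside is that the post-MBI rate then covers a year of clinical presentation plus a screen, while the Year 1 rate covers a screen only. The analysis is therefore conservative for MBI and should be described so.

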1.4 Molecular Breast Imaging as Functional Screening Tool

Molecular Breast Imaging (MBI) is a nuclear medicine technique utilizing a specialized gamma camera optimized for imaging the breast. MBI and MRI are both functional imaging techniques: whereas MRI exploits different vascular properties of tumors relative to normal breast tissue, MBI exploits heightened mitochondrial activity, leading to preferential uptake of ^{99m}Tc-sestamibi in breast tumors, regardless of surrounding breast density. Unlike older-generation scintillating gamma cameras (e.g. scintimammography or breast-specific gamma imaging), MBI employs solid-state cadmium zinc telluride (CZT) detectors in a dual-head configuration, allowing for improved count sensitivity, spatial resolution, energy resolution, and lesion detection, along with an attendant reduction in radiation dose.^{27,28}

In two prospective screening trials performed at Mayo Clinic Rochester by our team involving over 2500 asymptomatic women presenting for screening with dense breasts on previous mammogram, the addition of MBI to 2D digital mammography increased breast cancer detection almost four-fold.^{9,10} In the most recent trial, the ICDR of MBI was 8.8 per 1000. The ICDR was significantly increased for invasive cancers but not DCIS, suggesting that MBI detects clinically important cancers rather than contributing further to overdiagnosis. The majority of cancers detected by MBI were node negative, confirming its role in early detection. MBI also detected node positive and large cancers that were mammographically occult, thus unveiling the reservoir of potentially lethal cancers left undetected by mammography. MBI also demonstrates favorable false positive and biopsy rates relative to screening WBUS and MRI. The addition of MBI to mammography raised the recall rate by 6.6%. MBI is FDA-approved, clinically available at over 50 U.S. sites to date, less expensive than mammography (at our institution), and much less complex to interpret relative to WBUS or MRI.

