1.5 Significance of the Study

The significance of this study is that it will be the first prospective trial to compare MBI, a relatively low-cost functional breast imaging technique, to DBT, the new standard anatomic breast cancer screening technique in women with dense breasts. This study is also the first to evaluate two consecutive annual MBI scans to assess change in advanced cancer presentation after introduction of a functional imaging technique. These data will inform individualized decisions on supplemental screening and determine if a functional technique that is relatively low in cost and complexity of interpretation can eliminate the reservoir of clinically important breast cancers that remain occult on anatomic techniques. This study will also provide exploratory data about the optimal frequency of repeat MBI.

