5. IMAGING

5.1 Imaging Procedures

At Year 1 screening, all patients will undergo both DBT and MBI targeted to be performed on the same day if possible and required to be completed within three business days of each other prior to initiation of any diagnostic workup. All patients who did not receive a diagnosis of breast cancer during Year 1 will undergo subsequent annual MBI targeted to be performed at approximately one year (Year 2 screening) after Year 1 screening; and should be targeted for 335 to 455 days from Year 1 MBI screening. The Year 2 MBI should be scheduled within 3 business days of the Year 2 DBT if possible; completion of Year 2 DBT is encouraged but not required.

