8. STATISTICAL CONSIDERATIONS

8.1 Study Design

This study employs a paired design in which all participants will undergo both DBT and MBI for two rounds of annual screening, defined as Year 1 and Year 2. Unless otherwise specified, the primary unit of analysis will be the patient.

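### Item 4 credits MBI with any fall in advanced cancers from Year 1 to Year 2, but Year 1 is itself the first DBT+MBI round, so its rate already contains MBI's own first-round yield

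*Combined protocol and SAP*

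**What the plan says.** Section 2.2 item 4 gives the aim: "To assess the reduction in advanced cancer rate with incorporation of MBI screening". Section 8.6 item 4 gives the method: "the rate of advanced cancers detected at Year 2 screening will be compared to the rate at Year 1 screening". Each year's rate is to have a 95% confidence interval, and the two rates are compared with an exact two-proportion test. An advanced cancer is one larger than 2 cm and/or node positive; the definition does not depend on which test found it. Section 1.5 presents the two-round design as a way to "assess change in advanced cancer presentation after introduction of a functional imaging technique".

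On what happens at Year 1, Section 5.1 states: "At Year 1 screening, all patients will undergo both DBT and MBI". Section 8.1 confirms that there is no DBT-only group: "This study employs a paired design in which all participants will undergo both DBT and MBI for two rounds of annual screening". Prior MBI is an exclusion (Section 3.2, criterion 3). A positive MBI with a negative DBT may be worked up (Section 5.3), and the analysis set for each year requires both tests (Section 8.4).

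**The concern.** The aim is about the effect of introducing MBI, so a reader will take the Year 1 rate as the state of affairs before MBI. It is the result of the first DBT+MBI screen. Section 1.4 reports from the previous MBI trials that "MBI also detected node positive and large cancers that were mammographically occult". Cancers of that kind enter the Year 1 numerator. Once diagnosed, those women have no further study imaging (Sections 5.1 and 7), so the same cancers cannot appear at Year 2.

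A cancer already larger than 2 cm or node positive when MBI finds it has not been stopped from becoming advanced. Adding a more sensitive test raises the count in its first round and exhausts that pool before its second. Item 4 cannot separate this depletion from a real drop in advanced disease. What is at stake is a named secondary conclusion, that MBI reduces advanced cancer, which could be produced by MBI's own first-round yield.

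**Working it through.** **The plan's own figures.** Item 4 has no stated sample size, power or expected rate, so it has no figure to reproduce. The only powered calculation is for the primary endpoint (Section 8.7), and it reproduces. For a one-sided exact binomial test of 0.001 against 0.004 with n = 2631, the rejection limit is 7 or more cancers, the attained alpha is 0.0181 and the power is 0.9001 (0.8998 at n = 2630). Adding 375 gives 3006.

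**Inputs from Section 8.7, invasive cancers per 1000**
- D, DBT yield: 4.7 as quoted there, or 1.9 + 1.3 = 3.2 if the DBT increment is added to the 2D rate from the MBI study.
- M, extra yield from MBI: 4 (powered) to 5.6 (expected).

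**Assumptions, because the documents give no values**
- r: how often MBI-only cancers are advanced, relative to DBT-detected ones (1, 0.5 or 0.25).
- f: the fraction of the Year 1 MBI-only advanced yield seen again at Year 2 (0 or 0.5).
- s: the advanced share among DBT-detected cancers (25-40%), needed only for counts and tests.
- The DBT-detected advanced rate is the same in both years.

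**Apparent fall.** Year 1 rate = s(D + rM) and Year 2 rate = s(D + f·rM). The relative fall is rM(1 − f)/(D + rM), and s cancels.

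| r | D 4.7, M 4 | D 4.7, M 5.6 | D 3.2, M 4 | D 3.2, M 5.6 |
|---|---|---|---|---|
| 1 | 4/8.7 = 46.0% | 5.6/10.3 = 54.4% | 4/7.2 = 55.6% | 5.6/8.8 = 63.6% |
| 0.5 | 2/6.7 = 29.9% | 2.8/7.5 = 37.3% | 2/5.2 = 38.5% | 2.8/6.0 = 46.7% |
| 0.25 | 1/5.7 = 17.5% | 1.4/6.1 = 23.0% | 1/4.2 = 23.8% | 1.4/4.6 = 30.4% |

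The table is for f = 0. At f = 0.5 every entry halves, giving 23-32%, 15-23% and 9-15% for the three rows. At f = 1 there is no fall.

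**Counts.** With 2631 women per year and f = 0, expected Year 1 advanced cancers run from 0.25 × (3.2 + 0.25 × 4) × 2.631 = 2.8 to 0.40 × (4.7 + 5.6) × 2.631 = 10.8. Expected Year 2 counts run from 0.25 × 3.2 × 2.631 = 2.1 to 0.40 × 4.7 × 2.631 = 4.9.

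**Chance of declaring a fall.** I summed over both binomial distributions, treating the years as independent as the planned test does. I used a two-sided Fisher exact test at 0.05, f = 0, s = 25-40%, and all four D, M pairs.

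| r | Significant fall | Numerical fall |
|---|---|---|
| 1 | 7-28% | 76-94% |
| 0.5 | 2-9% | 62-79% |
| 0.25 | 1-3% | 52-63% |

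If the two years had equal rates, at the DBT-detected level, the significant fraction in this direction would be 0.3-1.1% and the numerical one 40-44%.

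**The case against.** The strongest defence is that the contrast is like for like in method: the same two tests, in the same kind of analysis set, one year apart. Section 1.5 says the idea is to clear a pool of cancers that anatomic imaging misses. Advanced cancers that DBT cannot see do exist under DBT-only screening, and a DBT-only reference would leave them out. This stands as a reason to keep the contrast. It does not justify attributing a fall to MBI, because depletion alone produces one.

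Item 3 of Section 8.6 already plans size and nodal status by modality, with summaries of lesions seen on one test only. The split can therefore be derived from planned output. But item 3 is descriptive and changes neither item 4's comparator nor its test.

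Item 4 is one of six secondary endpoints, without a power claim, and its confidence intervals will show the imprecision. That limits the consequence.

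A reader might infer that DBT-detected Year 1 against DBT-detected Year 2 is the unbiased comparison and should replace item 4. The documents do not support that. It drops Year 2 MBI-only advanced cancers, which favours MBI. It also still carries depletion: if an assumed 10-25% of the already advanced cancers that MBI removed at Year 1 would have surfaced on DBT by Year 2 (M = 4, D = 4.7, r = 1), the DBT rate falls by 0.10 × 4/4.7 = 9% to 0.25 × 4/4.7 = 21% with nothing prevented.

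**Conclusion.** The concern holds. The Year 1 reference contains MBI's own first-round advanced yield, so a fall to Year 2 is expected without any advanced cancer being prevented, provided MBI-only advanced cancers are less frequent in the second round than in the first. The bias favours MBI.

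Only the direction can be settled from the documents. The 46-64%, 30-47% and 18-30% ranges are illustrations. They rest on an unchanged DBT-detected rate, no MBI-only advanced cancers at Year 2, and an assumed ratio of advanced shares. The no-recurrence assumption is the extreme case.

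A reader might infer that the plan will often yield a falsely significant reduction. That goes too far. The upper figure of 28% needs equal advanced shares, the lower DBT yield, the larger MBI yield, a 40% advanced share and no recurrence; at a quarter of the share the figure is 1-3%. With about 2-11 expected events per year, an imprecise numerical fall is the likelier product. The 2631 women per year is also an assumption: Section 5.1 does not require Year 2 DBT, so the Year 2 set may be smaller.

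Nor do the documents show that a real reduction is absent. Item 4 simply cannot tell the two apart. The primary endpoint does not use this contrast and is unaffected. The change should be made.

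**What to change.** In Section 8.6 item 4, with matching wording in Section 2.2 item 4 and Section 1.5:

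1. Report advanced cancers for each year by detecting modality (DBT-detected and MBI-only), each with an exact 95% confidence interval.
2. Label the all-modality Year 2 versus Year 1 contrast as second versus first MBI round, and state that it is not interpreted as a reduction due to MBI.
3. Add the DBT-detected Year 1 versus Year 2 comparison as a supportive analysis, not the main one. State that it omits Year 2 MBI-only cancers and is still affected by the removal at Year 1 of cancers that MBI found.

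No new data are needed: the two tests are read blinded and recorded separately (Section 5.2), and cancers are matched to findings by modality (Section 8.3). The cost is one more table, few events on each line, and a weaker stated conclusion for this endpoint.
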